4.3 Intervention

The primary aim is to assess the efficacy of ixazomib for the prevention of recurrent or late grade II-IV aGVHD or chronic GVHD at 1-year post-transplant. The accrual period will be approximately 3 years with an additional 12 months of follow-up after the accrual period has been completed. Stopping rules are in place for secondary graft failure without autologous recovery and excessive treatment related toxicity. The target sample size for this study is 46 patients with an approximate accrual of 16 patients per year.

5.0 THERAPEUTIC/DIAGNOSTIC AGENTS

If appropriate describe packaging, labeling and storage requirements of the agents and/or device(s). Indicate any special instructions for maintaining, tracking and monitoring that is required by sponsor, FDA and/or MSKCC.

5.1 MLN 9708 (Ixazomib)

Supplied as: strengths of 4.0-, 3.0-, and 2.3-mg and 2.0-, 0.5-, and 0.2 mg capsules as the active boronic acid. The study drug will be supplied by Takeda Pharmaceuticals/ Millennium

as capsules of 0.2-, 0.5-, and 2.0 mg, or as capsules of 2.3-, 3.0- and 4.0 mg ixazomib. This is dependent on available ixazomib formulation.

Reconstitution directions: N/A.

Storage and stability: on receipt at the investigative site, study drug should remain in the blister and carton provided until use or dispensation. The container should be stored refrigerated (36°F to 46°F, 2°C to 8°C). All excursions should be brought to the sponsor's attention for assessment and authorization for continued use. Ensure that the drug is used before the retest expiry date provided by Takeda Pharmaceuticals/ Millennium. Expiry extensions will be communicated accordingly with updated documentation to support the extended shelf life.

Study drug dispensed to the patient for take-home dosing should remain in the listed packaging and carton and refrigerated as noted above until the point of use. Comprehensive instructions should be provided to the patient in order to ensure compliance with dosing procedures. Patients should be instructed to store the medication refrigerated (36°F to 46°F, 2°C to 8°C) for the duration of each cycle. Patients should be instructed to return their empty carton to the investigative site, rather than discarding them.

Reconciliation will occur accordingly when the patient returns for their next cycle of take-home medication. Any extreme in temperature should be reported and dealt with on a case-by-case basis.

Preparation: Patients should be instructed to swallow ixazomib capsules whole, with water, and not to break, chew, or open the capsules. Study drug should be taken on an empty stomach (no food or drink) at least 1 hour before or 2 hours after a meal. Each capsule should be swallowed separately with a sip of water.

Clinical considerations: Missed doses can be taken as soon as the patient remembers if the next scheduled dose is 72 hours or more away. A double dose should not be taken to make up for a missed dose. If the patient vomits after taking a dose, the patient should not repeat the dose but should resume dosing at the time of the next scheduled dose.

Hydration: A total of approximately 8 ounces (240 mL) of water should be taken with the capsules.

Toxicities: see section 11.0

Incompatibilities: with strong inhibitors of CYP1A2 (fluvoxamine, enoxacin, ciprofloxacin), strong inhibitors of CYP3A (clarithromycin, telithromycin, itraconazole, voriconazole, ketoconazole, nefazodone, posaconazole), or strong CYP3A inducers (rifampin, rifapentine, rifabutin, carbamazepine, phenytoin, phenobarbital), or use of Ginkgo biloba or St. John's wort.

6.1 CRITERIA FOR SUBJECT ELIGIBILITY

Describe the characteristics of the patient/subject population.

6.2 Subject Inclusion Criteria

Eligible patients will be consented by the Adult BMT service attending. All patients must meet all of the following inclusion criteria to be enrolled in the study:

All patients must meet all of the following inclusion criteria to be enrolled in the study:

- Patients 18 years or older.
- Diagnosis: myeloid or lymphoid hematologic malignancy treated with a RI or NMA conditioning HSCT who received calcineurin inhibitor based drug (for example: tacrolimus or cyclosporin) and methotrexate as part of their initial GVHD prophylaxis. Patients who received sirolimus as part of their GVHD prophylaxis will be eligible.
- Recipients of 8-7/8 HLA-matched donor. Post-HSCT period within day +100 to day +150.
- Female patients who:
 - Are postmenopausal for at least 1 year before the screening visit, OR
 - Are surgically sterile, OR
 - If they are of childbearing potential, agree to practice 2 effective methods of contraception, at the same time, from the time of signing the informed consent form through 90 days after the last dose of study drug, OR
 - Agree to practice true abstinence when this is in line with the preferred and usual lifestyle of the subject (periodic abstinence and withdrawal are not acceptable methods of contraception).
- Male patients, even if surgically sterilized (i.e. Status post-vasectomy) must agree to one of the following:
 - Agree to practice effective barrier contraception during the entire study treatment period and through 90 days after the last dose of study drug, OR
 - Agree to practice true abstinence when this is in line with the preferred and usual lifestyle of the subject (periodic abstinence and withdrawal are not acceptable methods of contraception).

Organ Function and Performance Status Criteria:

- Karnofsky score \geq 70 %
- Absolute neutrophil count (ANC) \geq 1000/mm³ and platelet count \geq 75,000/mm³. Platelet transfusions to help patients meet eligibility criteria are not allowed within 3 days before study enrollment.
- Calculated creatinine clearance \geq 30 mL/min (based on the Cockcroft and Gault method)
- Total bilirubin \leq 1.5 x upper limit of normal range (ULN).
- AST/ALT \leq 3 x ULN (unless benign congenital hyperbilirubinemia).
- Hemoglobin $>$ 8.0 g/dL. Red blood cell transfusions to help patients meet eligibility criteria are not allowed within 3 days before study enrollment.

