6.3 Subject Exclusion Criteria

- Disease: evidence of progressive disease at the time of study enrollment.
- Prior Therapy: one or more prior allogeneic stem cell transplantation (prior autologous transplant is acceptable).
- Active acute or chronic GVHD.
- Active and uncontrolled infection.
- Pregnant or breast feeding.
- Major surgery within 14 days before enrollment.

- Evidence of current uncontrolled cardiovascular conditions, including uncontrolled hypertension, uncontrolled cardiac arrhythmias, symptomatic congestive heart failure, unstable angina, or myocardial infarction within the past 6 months.
- Systemic treatment, within 14 days before the first dose of ixazomib, with strong inhibitors of CYP1A2 (fluvoxamine, enoxacin, ciprofloxacin), strong inhibitors of CYP3A (clarithromycin, telithromycin, itraconazole, voriconazole, ketoconazole, nefazodone, posaconazole) or strong CYP3A inducers (rifampin, rifapentine, rifabutin, carbamazepine, phenytoin, phenobarbital), or use of Ginkgo biloba or St. John's wort.
- Any serious medical or psychiatric illness that could, in the investigator's opinion, potentially interfere with the completion of treatment according to this protocol.
- Patient or guardian unable to give informed consent or unable to comply with the treatment protocol including appropriate supportive care, follow-up and research tests.
- Patients with known allergy to boron or boron-containing products, or excipients in the various formulations of any agent.
- Known GI disease or GI procedure that could interfere with the oral absorption or tolerance of ixazomib including difficulty swallowing.
- Diagnosed or treated for another malignancy within 2 years before study enrollment or previously diagnosed with another malignancy and have any evidence of residual disease. Patients with nonmelanoma skin cancer or carcinoma in situ of any type are not excluded if they have undergone complete resection.
- Patient with \geq Grade 3 peripheral neuropathy, or Grade 2 with pain on clinical examination during the screening period.
- Received post-transplant cyclophosphamide

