9.1.1 Dose-modification guidelines

Treatment with ixazomib will use a cycle length of 28 days. For a new cycle of treatment to begin, the patient must meet the following criteria:

- ANC \geq 1,000/mm³
- Platelet count \geq 75,000/mm³
- Serum creatinine \leq 2.5 mg/dL and less than double from pre-treatment evaluation value

If the patient fails to meet the above-cited criteria for initiation of the next cycle of treatment, dosing should be delayed for 1 week. At the end of that time, the patient should be re-evaluated to determine whether the criteria have been met. If the patient continues to fail to meet the above-cited criteria, delay therapy and continue to re evaluate. The maximum delay before treatment should be discontinued will be 4 weeks or at the discretion of the Principal Investigator.

Ixazomib dose adjustments:

Dose Level	Dose (mg)
Starting Dose	4.0 mg
-1	3.0 mg
-2	2.3 mg

Table 9.1.1 Ixazomib dose adjustments for hematologic toxicities

Criteria	Action
Within-Cycle Dose Modifications	

 If platelet count $\leq 30 \times 10^9/L$ or ANC $\leq 0.50 \times 10^9/L$ on ixazomib dosing day (other than Day 1) If serum creatinine $> 2.5 \text{ mg/dL}$ or has doubled from pre-treatment evaluation 	
 Ixazomib dose should be withheld. Complete blood count (CBC) with differential should be repeated until the ANC and/or platelet counts have exceeded the prespecified values. Upon recovery, ixazomib may be reinitiated with 1 dose level reduction.
Dose Modifications for Subsequent Treatment Cycles	

 Delay of > 2 weeks in the start of a subsequent cycle due to lack of toxicity recovery as defined in Section 9.1.1 ANC $< 1.0 \times 10^9/L$, platelet count $< 75 \times 10^9/L$, serum creatinine $> 2.5 \text{ mg/dL}$, serum creatinine doubled from pre-treatment evaluation, or other nonhematologic toxicities $>$ Grade 1 or not to the patient's baseline condition 	
 Hold ixazomib until resolution as per criteria Section 9.1.1 Upon recovery, reduce ixazomib 1 dose level. The maximum delay before treatment should be discontinued will be 3 weeks or at the discretion of the PI.
Dose Modifications for Subsequent Treatment Cycles	

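### The benign congenital hyperbilirubinemia exemption is attached to the AST/ALT limit, and the bilirubin limit has no exemption

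*Combined protocol and SAP*

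**What the plan says.** Section 6.2 (Subject Inclusion Criteria) opens with a conjunctive rule: "All patients must meet all of the following inclusion criteria to be enrolled in the study". Under "Organ Function and Performance Status Criteria" it then lists two adjacent liver bullets:

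- Total bilirubin at most "1.5 x upper limit of normal range (ULN"). The bullet ends there, with no exception.
- AST/ALT at most "3 x ULN (unless benign congenital hyperbilirubinemia"). No alternative ceiling is given for a patient who falls under the exception.

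The rule is enforced. Section 15.2 requires a signed, protocol-specific eligibility checklist, and Section 13.0 removes a patient who is found ineligible at any time.

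**The concern.** The condition named in the exemption is, by its name, one of bilirubin, yet it lifts the limit on a different analyte. Two things follow. The entry limit on transaminases disappears for patients with the condition, although nothing in its name explains a raised AST or ALT. And the bilirubin limit, which the condition could well breach, still applies to them in full.

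The stakes are safety at entry and uniform application of the criteria. The two liver bullets are the only numerical liver limits the protocol sets for entry. Section 3.0 names the liver as an acute GVHD target organ, and Section 12.3.1 asks assessors to weigh possible confounding factors, so abnormal liver tests at entry add something to disentangle. Two investigators could also sort the same patient differently, one following the text and one the presumed intent. The second would then have enrolled a patient whom Section 13.0 requires to be removed.

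**Working it through.** No arithmetic applies, and the plan has no figure to reproduce on this point. The check is the logic of the two bullets, followed by a search for any other clause that changes the result.

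**Rule as written.** Let B be total bilirubin and T be AST/ALT, both as multiples of ULN, and let C mean that the patient has benign congenital hyperbilirubinemia. Because all criteria must be met:

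liver criteria met = (B ≤ 1.5) AND (T ≤ 3 OR C)

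**Applied to cases.** The values 2 and 8 are illustrative and are not in the protocol.

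| Case | C | B | T | Bilirubin bullet | AST/ALT bullet | Liver criteria |
|---|---|---|---|---|---|---|
| 1 | yes | ≤ 1.5 | 8 | met | waived | met |
| 2 | yes | 2 | normal | not met | met | not met |
| 3 | yes | ≤ 1.5 | ≤ 3 | met | met | met |
| 4 | no | ≤ 1.5 | 8 | met | not met | not met |
| 5 | no | 2 | normal | not met | met | not met |

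Cases 1 and 2 show the defect. In case 1, T could be any multiple with the same result. Cases 3 to 5 come out as they would without the exemption.

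**With the exemption on the bilirubin bullet.** The rule becomes (B ≤ 1.5, or C within whatever limit the sponsor states) AND (T ≤ 3). Case 1 is then not met. Case 2 is met, subject to any such limit. Cases 3 to 5 do not change.

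**Other clauses that might catch case 1.**

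- Section 6.3 excludes active GVHD, uncontrolled active infection, and "Any serious medical or psychiatric illness that could, in the investigator's opinion, potentially interfere with the completion of treatment according to this protocol". These can stop enrollment, but none carries a liver value.
- Section 9.1.1 says "For a new cycle of treatment to begin, the patient must meet the following criteria" and then lists ANC, platelets and serum creatinine. No liver test is listed.
- Table 9.1.1 holds drug before later cycles for other non-hematologic toxicity above grade 1 or not back to the patient's baseline. It does not govern the first dose, and a stable elevation present at entry may count as that baseline.
- Table 11.2 has no liver-specific row. Its general row holds drug for non-hematologic toxicity of grade 3 or higher judged related to study drug, until recovery to grade 1 or lower or to baseline.
- Section 10.0 schedules blood chemistry before each cycle and before the third dose of cycles 1 and 2, but attaches no liver threshold to the results.

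**Extraction error.** This is unlikely. The bilirubin bullet ends with its own full stop, and the parenthesis sits inside the AST/ALT bullet.

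**The case against.** The strongest reply is that little harm can follow. Case 1 needs a patient with the congenital condition, bilirubin within the limit, AST/ALT above 3 x ULN, no active GVHD or uncontrolled infection, and an attending physician who is not concerned. Section 6.3 gives that physician grounds to refuse, chemistry is repeated during treatment, and Table 9.1.1 would act on worsening. This stands as a limit on size. A reader might infer that nothing later catches such a patient; the documents do not support that, because these partial backstops exist. What they lack is a numerical liver limit at entry.

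A second reply is that the intent is nowhere stated. That is right: placing the exemption with bilirubin is an inference, though it is the placement under which the exemption relates to the quantity being measured.

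A third is that moving the words unchanged would leave the bilirubin limit waived without bound, and that a raised baseline bilirubin could itself confuse liver GVHD assessment, since Section 3.0 lists jaundice among the presenting signs. Both points stand, and the correction has to deal with them.

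**Conclusion.** The criterion is wrong as written. It waives the AST/ALT limit for patients with benign congenital hyperbilirubinemia and withholds any bilirubin exemption from them. Because the rule is certified by checklist and ineligibility leads to removal, it affects who enters the trial.

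The scope is narrow. The AST/ALT limit is lost only for patients with the condition, and such patients are shut out only if their bilirubin exceeds 1.5 x ULN. The documents give no prevalence, so the number affected is unknown; that it is small is a judgment.

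Two stronger readings are tempting and are not supported:

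- That the primary result is at risk. Section 14.0 requires at least 23 of 46 patients free of the GVHD endpoint. One misclassified patient shifts the count by one, so it changes that final decision only if the true count is 22 or 23. No document figure shows that an affected patient would enroll and also be misclassified.
- That a patient admitted under the waiver has unexplained liver injury. This is possible, but the text does not establish it.

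Sample size, error rates and the planned analyses are untouched. The conclusion rests on the literal text of the two bullets; only the direction of the correction rests on the inferred intent.

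**What to change.** Amend Section 6.2 so that the two bullets are reconciled:

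1. Attach the exemption to the total bilirubin criterion, and let the existing AST/ALT limit apply to all patients.
2. Have the sponsor state what bilirubin limit, if any, applies to exempted patients. No value is proposed here.
3. Record each exempted patient's baseline bilirubin and make it available to GVHD assessors, so that it is not read as new liver GVHD.
4. Update the eligibility checklist to match.

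The cost is a one-line amendment and a checklist change. No extra test is needed, because bilirubin must already be measured to judge eligibility. The downside is that exempted patients enter with a raised baseline bilirubin, which has to be taken into account whenever liver GVHD is assessed.

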6.3 Subject Exclusion Criteria

- Disease: evidence of progressive disease at the time of study enrollment.
- Prior Therapy: one or more prior allogeneic stem cell transplantation (prior autologous transplant is acceptable).
- Active acute or chronic GVHD.
- Active and uncontrolled infection.
- Pregnant or breast feeding.
- Major surgery within 14 days before enrollment.

- Evidence of current uncontrolled cardiovascular conditions, including uncontrolled hypertension, uncontrolled cardiac arrhythmias, symptomatic congestive heart failure, unstable angina, or myocardial infarction within the past 6 months.
- Systemic treatment, within 14 days before the first dose of ixazomib, with strong inhibitors of CYP1A2 (fluvoxamine, enoxacin, ciprofloxacin), strong inhibitors of CYP3A (clarithromycin, telithromycin, itraconazole, voriconazole, ketoconazole, nefazodone, posaconazole) or strong CYP3A inducers (rifampin, rifapentine, rifabutin, carbamazepine, phenytoin, phenobarbital), or use of Ginkgo biloba or St. John's wort.
- Any serious medical or psychiatric illness that could, in the investigator's opinion, potentially interfere with the completion of treatment according to this protocol.
- Patient or guardian unable to give informed consent or unable to comply with the treatment protocol including appropriate supportive care, follow-up and research tests.
- Patients with known allergy to boron or boron-containing products, or excipients in the various formulations of any agent.
- Known GI disease or GI procedure that could interfere with the oral absorption or tolerance of ixazomib including difficulty swallowing.
- Diagnosed or treated for another malignancy within 2 years before study enrollment or previously diagnosed with another malignancy and have any evidence of residual disease. Patients with nonmelanoma skin cancer or carcinoma in situ of any type are not excluded if they have undergone complete resection.
- Patient with \geq Grade 3 peripheral neuropathy, or Grade 2 with pain on clinical examination during the screening period.
- Received post-transplant cyclophosphamide

7.0 RECRUITMENT PLAN

Patients who meet the eligibility criteria as listed in Section 6.0 will be recruited for this study by an Attending Physician of the Adult BMT service. This protocol will take due notice of NIH/ADAMHA policies concerning inclusion of women and minorities in clinical research populations.

8.1 PRETREATMENT EVALUATION

8.1 Pretreatment evaluation

The following tests must be performed prior to study drug treatment starts. Tests that are performed within 30 days prior to consent are not required to be repeated:

- Complete history, review of systems, physical exam (including performance status)
- CBC with differential, comprehensive metabolic panel (CMP), thyroid function test (TSH and free T4)
- EKG
- Urinalysis
- Pregnancy test (required only for females of childbearing age)
- Immune function tests (testing is performed following institutional practice and is recommended before starting treatment with ixazomib)

9.1 TREATMENT/INTERVENTION PLAN

Patients will be cared and monitor according to the allogeneic BMT clinical care guidelines.
https://one.mskcc.org/sites/pub/corp/bmt/Documents/H3_Allo%20Guidelines_01_27_2016.pdf

Patients will have received a calcineurin inhibitor based GVHD prophylaxis with either tacrolimus or cyclosporin in combination with methotrexate. The study drug will be initiated between day 100 to 150 post-allograft.

Tapering of calcineurin inhibitor (CNI) will follow the institutional practice. For recipients of HLA-matched sibling donor, is recommended to initiate CNI taper around day 100 and taper at 10-25% decrements every 2 weeks. For recipients of HLA-matched unrelated and HLA-mismatched unrelated donors, is recommended to initiate CNI taper around day 180 and taper at 10-15% decrements in 4 weeks intervals.

9.2 GVHD prophylaxis

Ixazomib beginning between day +100 to +150 at a dose of 4 mg orally once per week (3 weeks on/ 1 week off). The patients will continue on this same dose until taper off from immunosuppressants or 1 year post-HSCT is reached (whichever occurs first) or until the patient develops GVHD or malignant disease relapse/progression occurs. Patients who reach 1 year post-HSCT or discontinue immunosuppressants mid-cycle should complete their current cycle of ixazomib.

- The levels of the drug will not be monitored while the patients are on study.
- In order for patients to receive drug, they must have a platelet count > 75K, Hgb (untransfused) > 8 and an ANC > 1.0 (can be supported with G-CSF)
- If more than 2 doses in a row or more than 3 doses total are held, the patient is removed from study.
- Doses are given weekly +/- 3 days

9.1.1 Dose-modification guidelines

Treatment with ixazomib will use a cycle length of 28 days. For a new cycle of treatment to begin, the patient must meet the following criteria:

- ANC \geq 1,000/mm³
- Platelet count \geq 75,000/mm³
- Serum creatinine \leq 2.5 mg/dL and less than double from pre-treatment evaluation value

If the patient fails to meet the above-cited criteria for initiation of the next cycle of treatment, dosing should be delayed for 1 week. At the end of that time, the patient should be re-evaluated to determine whether the criteria have been met. If the patient continues to fail to meet the above-cited criteria, delay therapy and continue to re evaluate. The maximum delay before treatment should be discontinued will be 4 weeks or at the discretion of the Principal Investigator.

Ixazomib dose adjustments:

Dose Level	Dose (mg)
Starting Dose	4.0 mg
-1	3.0 mg
-2	2.3 mg

Table 9.1.1 Ixazomib dose adjustments for hematologic toxicities

Criteria	Action
Within-Cycle Dose Modifications	

 If platelet count $\leq 30 \times 10^9/L$ or ANC $\leq 0.50 \times 10^9/L$ on ixazomib dosing day (other than Day 1) If serum creatinine $> 2.5 \text{ mg/dL}$ or has doubled from pre-treatment evaluation 	
 Ixazomib dose should be withheld. Complete blood count (CBC) with differential should be repeated until the ANC and/or platelet counts have exceeded the prespecified values. Upon recovery, ixazomib may be reinitiated with 1 dose level reduction.
Dose Modifications for Subsequent Treatment Cycles	

 Delay of > 2 weeks in the start of a subsequent cycle due to lack of toxicity recovery as defined in Section 9.1.1 ANC $< 1.0 \times 10^9/L$, platelet count $< 75 \times 10^9/L$, serum creatinine $> 2.5 \text{ mg/dL}$, serum creatinine doubled from pre-treatment evaluation, or other nonhematologic toxicities $>$ Grade 1 or not to the patient's baseline condition 	
 Hold ixazomib until resolution as per criteria Section 9.1.1 Upon recovery, reduce ixazomib 1 dose level. The maximum delay before treatment should be discontinued will be 3 weeks or at the discretion of the PI.
Dose Modifications for Subsequent Treatment Cycles	

 All hematologic toxicities 	
 For hematologic toxicity that occurs during a cycle but recover in time for the start of the next cycle,: 
 If dose was reduced within the cycle, start the next cycle at that same dose. If due to toxicity timing, i.e. after Day 15 dosing thus a dose reduction was not required at that point in the cycle, reduce ixazomib by 1 dose level at the start of that cycle. Do not reduce the dose both within a cycle and at the start of the cycle for the same most severe toxicity.

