11.2 Ixazomib

Ixazomib may cause fatigue, thrombocytopenia, nausea, vomiting, diarrhea, decreased appetite. Less frequently the drug can cause rash, peripheral edema, and neutropenia. Further details of management of ixazomib-related hematologic toxicity AEs are described in Section 9.1.1.

Treatment modifications due to ixazomib-related AEs are outlined in Table 11.2.

Table 11.2 Ixazomib treatment modification (delays, reductions, and discontinuations) due to adverse events (non-hematologic toxicities)

Adverse Event (Severity)	Action on Study Drug	CTCAE Description
Peripheral Sensory		
Neuropathy:		
Grade 1 peripheral sensory neuropathy	
 • No action 	Grade 1: Asymptomatic; loss of deep tendon reflexes or paresthesia
Grade 2 peripheral sensory neuropathy	
 • Hold study drug until resolution to Grade ≤ 1 or baseline • Once recovered, resume study drug at same dose 	Grade 2: Moderate symptoms; limiting instrumental ADL
Grade 3 peripheral sensory neuropathy	
 • Hold study drug until resolution to Grade ≤ 1 or baseline • Reduce study drug to next lower dose upon recovery 	Grade 3: Severe symptoms; limiting self care ADL
Grade 4 peripheral sensory neuropathy	
 • Discontinue study drug 	Grade 4: Life-threatening consequences; urgent intervention indicated
Nervous System Disorder:		
Grade 1 nervous system toxicity judged to be related to study drug	
 • No action 	Grade 1: Asymptomatic or mild symptoms; clinical or diagnostic observations only; intervention not indicated
Grade 2 nervous system toxicity judged to be related to study drug	
 • Hold study drug until resolution to Grade ≤ 1 or baseline 	Grade 2: Moderate; minimal, local or noninvasive intervention indicated; limiting age appropriate instrumental ADL
New or worsening grade 2 or grade 3 or 4 toxicity judged to be related to study drug	
 • Discontinue study drug 	Grade 3: Severe or medically significant but not immediately life-threatening; hospitalization or prolongation of existing hospitalization indicated; disabling; limiting self care ADL

Table 11.2 Ixazomib treatment modification (delays, reductions, and discontinuations) due to adverse events (non-hematologic toxicities)

Adverse Event (Severity)	Action on Study Drug	CTCAE Description

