		Grade 4: Life-threatening consequences; urgent intervention indicated
Grade 2 Rash	
• Symptomatic recommendations. The investigator and project clinician may discuss considerations for dose modifications and symptom management.	Grade 2: Rash covering 10-30% BSA with or without symptoms; limiting instrumental ADL
Grade \geq 3 nonhematologic toxicity judged to be related to study drug	
• Hold study drug until resolution to Grade \leq 1 or baseline• Reduce study drug to next lower dose upon recovery	
If not recovered to Grade \leq 1 or baseline within 4 weeks	
• Discontinue treatment	

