12.3 Criteria for treatment failure for the primary endpoint

- Study drug is discontinued and unable to resume due to drug related toxicity.
- New onset or recurrence of grade II-IV aGVHD (including GVHD flares).
- New onset of chronic GVHD.
- Administration of systemic therapy for treatment of GVHD.
- Development of secondary graft failure during the administration of the study drug.
- Mortality (transplant or treatment-related)

If treatment failure criteria is met, the patient will be removed from the study. A 30-day follow-up will be conducted for end-of-treatment evaluation for toxicity assessment. This follow-up may be conducted via phone call or in-person by the clinical team.

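### Tables 9.1.1 and 11.2 give different dose actions for the same Grade 2 nonhematologic toxicity at a cycle start, and the protocol does not say which table governs

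*Combined protocol and SAP*

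**What the plan says.** Four places bear on the dose at the start of cycle 2 or later.

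- **Section 9.1.1, text.** A new cycle needs adequate ANC, platelets and creatinine. If these are not met, "dosing should be delayed for 1 week. At the end of that time, the patient should be re-evaluated". No nonhematologic criterion is listed and no change of dose level is mentioned.
- **Table 9.1.1, subsequent-cycle rows.** The title limits the table to hematologic toxicity. One row, however, combines a delay of more than 2 weeks, the ANC, platelet and creatinine limits, and other nonhematologic toxicity above "Grade 1 or not to the patient's baseline condition". The action is to hold until the Section 9.1.1 criteria are met, and then "Upon recovery, reduce ixazomib 1 dose level". Treatment stops after a 3-week delay unless the PI decides otherwise.
- **Table 11.2 (Section 11.2).** This is the nonhematologic table. After Grade 2 sensory neuropathy: "Once recovered, resume study drug at same dose". For Grade 2 rash: "The investigator and project clinician may discuss considerations for dose modifications and symptom management". The general hold-and-reduce row starts at Grade 3 and requires a judgement that the toxicity is drug-related.
- **Section 12.3.** One criterion for primary-endpoint failure is "Study drug is discontinued and unable to resume due to drug related toxicity". Section 14.0 confirms that the non-GVHD failure criteria count in the primary endpoint.

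**The concern.** Table 9.1.1 and Table 11.2 both cover Grade 2 nonhematologic toxicity present when a cycle is due, and their instructions differ. Toxicity is assessed before the first dose of every cycle (Section 10.0, schedule footnote 4), which is when the two tables diverge.

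The cross-references do not resolve this. The introduction to Section 9.2 (Management of clinical events) names diarrhea, fatigue, nausea, vomiting and rash among the expected reactions and sends the reader to Section 9.1.1 for further management detail. Section 11.2 refers only hematologic toxicity to Section 9.1.1. A clinician who follows the first reference reaches a rule that Table 11.2 contradicts.

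Table 9.1.1 also leaves nonhematologic recovery undefined. It holds drug until the Section 9.1.1 criteria are met, and those criteria cover only ANC, platelets and creatinine.

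At stake are the dose a patient receives, safety, and, by one route, whether the patient counts as a primary-endpoint failure.

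**Working it through.** **1. Grade 2 sensory neuropathy that resolves, in a patient on 4.0 mg who entered without neuropathy.** The dose levels in Section 9.1.1 are 4.0, 3.0 and 2.3 mg.

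- Table 9.1.1: hold, then one level down, to 3.0 mg.
- Table 11.2: hold, then the same dose, 4.0 mg.
- Difference: (4.0 − 3.0)/4.0 = 25%.

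The Table 9.1.1 row can be read in two ways. If the toxicity list stands alone, the conflict exists from Day 1 of the cycle. If the list only explains what counts as failure to recover, the reduction follows only a delay of more than 2 weeks. On that reading the conflict remains for neuropathy that resolves after 2 weeks but before the maximum delay. The neuropathy conflict survives both readings.

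**2. Persistent drug-related Grade 2 fatigue.**

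- Table 9.1.1: above Grade 1, so hold. Without recovery, treatment stops at 3 weeks unless the PI uses discretion. Discontinuation for drug-related toxicity without resumption is a failure under Section 12.3.
- Table 11.2: fatigue has no row of its own and Grade 2 is below the general Grade 3 threshold, so no hold is ordered and treatment continues.

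This takes the last row of Table 11.2 (discontinue if not recovered within 4 weeks) as belonging to the Grade 3 row directly above it. The Section 9.1.1 text gives a different limit: "The maximum delay before treatment should be discontinued will be 4 weeks or at the discretion of the Principal Investigator". That 3-week versus 4-week mismatch is a separate discrepancy; the route above needs only that one table holds drug and the other does not.

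**3. Day 1 ANC, platelet or creatinine miss that recovers after 1 week.** The text says delay and re-evaluate. Table 9.1.1 reduces one level if its list stands alone, and does not reduce if a delay of more than 2 weeks is also required. The documents do not say which is meant.

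**4. What a change in failure status would do to the design.** Section 14.0 continues if at least 8 of the first 18 patients are failure-free and calls the regimen promising if at least 23 of 46 are. With p the failure-free probability:

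P(promising) = Σ (x = 8 to 18) P(Bin(18, p) = x) × P(Bin(28, p) ≥ 23 − x)

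At p = 0.40 this is 0.0952 and at p = 0.60 it is 0.9004. This reproduces the stated errors of 0.10, and the design is not in question.

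The documents give no number of affected patients, so the following is an illustration on an assumed range. It supposes that the stricter rule adds k expected failures per 46 patients:

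- k = 1: p = 0.60 − 1/46 = 0.578, power 0.845
- k = 2: p = 0.60 − 2/46 = 0.557, power 0.771
- k = 3: p = 0.60 − 3/46 = 0.535, power 0.680

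Extra failures lower the chance of success under the null as well. At p = 0.40 − 0.02 it is 0.056. The stricter rule would therefore cost power and would not inflate the type I error.

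**The case against.** The best defence is that the documents divide the tables by scope. Table 9.1.1 is titled for hematologic toxicity and Table 11.2 for nonhematologic toxicity, and Section 11.2 says as much. Table 11.2 also has specific entries for neuropathy and rash, against a single residual clause in Table 9.1.1. This shows what was probably intended. It does not settle the matter, because Table 9.1.1 names nonhematologic toxicity outright, Section 9.2 sends such events to Section 9.1.1, and no precedence is stated.

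Several stronger readings are tempting, and the documents do not support them:

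- *That any Day 1 count or creatinine miss forces a reduction.* The row as extracted shows no markers separating its parts, so this is one reading and not a fact.
- *That the Section 9.1.1 text is a third contradictory dose rule.* It sets timing and is silent on dose level, and a table that adds a dose action can be supplementing it.
- *That a patient who uses up both reduced levels becomes a failure.* No section says what follows level −2, and a dose reduction is not itself a failure under Section 12.3.
- *That the all-grade rates in Section 3.2.1.2 (nausea 53%, fatigue 51%, diarrhea 44%) size the problem.* They are not rates of Grade 2 toxicity at a cycle start.
- *That this creates variation between sites.* Patients are enrolled and followed by one institution's BMT service. The variation would be between treating clinicians or between patients.

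PI discretion does soften the delay limits, but it also puts case-by-case judgement into a component of the primary endpoint.

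**Conclusion.** The point holds as an inconsistency of wording, of moderate severity. The two tables conflict on Grade 2 nonhematologic toxicity at a later cycle start, most clearly for sensory neuropathy, where the restart dose differs by 25% under either reading of the Table 9.1.1 row. Failure status can also differ, but by a narrower route: persistent, drug-related Grade 2 toxicity, a hold under Table 9.1.1, and no use of PI discretion. If the Table 9.1.1 row applies only after a long delay, that route further requires that nonhematologic toxicity counts as a reason to delay the cycle.

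The effect on the trial's result cannot be derived from the documents. The power figures show only that, with 46 patients, a few reclassified outcomes would matter. They are not an estimate of how many there would be. A reader might infer that the two-stage design is wrong or that a false positive becomes more likely; the calculation supports neither.

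**What to change.** Reconcile Section 9.1.1, Table 9.1.1, Section 9.2 and Table 11.2 so that each toxicity type has one governing table. Specifically:

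- Align or remove the nonhematologic clause in Table 9.1.1.
- Define the nonhematologic recovery criterion for restarting.
- State whether the toxicity must be judged drug-related.
- State whether a Day 1 ANC, platelet or creatinine miss alone, or only a delay of more than 2 weeks, triggers the one-level reduction, and make the Section 9.1.1 text agree.
- Correct the cross-reference in the introduction to Section 9.2 (Management of clinical events).

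The same edit should settle the 3-week and 4-week limits. It should also say whether delayed doses count toward the held-dose removal rule in Section 9.2 (GVHD prophylaxis), and whether that removal is a failure.

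Which action stands is for the clinical team, and this review takes no position on it. The cost is a wording amendment, with no extra patients or procedures.
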